## 9. HANDLING OF MISSING DATA

### Imputation of Start and End Dates of Adverse Event (AE)

To calculate duration of Adverse Events, the following rules will be used where applicable to impute partial or completely missing start dates or end dates:

- If only the day is missing for a start date, the 1st of the month will be imputed. If the new estimated date falls before the date of first dose, while the known month and year match the month and year of the first dose, the date of first dose will be used as the new estimated date. The AE will be considered as a treatment-emergent AE (TEAE).
- If only the day is missing for an end date, the last day of the month will be imputed. If the new estimated date falls after the date of last study visit, the date of last study visit will be used as the new estimated date. Last study visit is defined as the Week 12 visit for those who elect to participate in the open-label long-term study, or the Week 16 Follow-up visit for those who fail to qualify for participation in the open-label study, or who qualify to participate but ultimately elect not to enroll.
- If both the day and the month are missing for a start date or end date, no imputation will be used, and the duration will not be calculated. However, if the year of start is the same or greater than the year of the first dose date, the AE will be considered as treatment emergent.

- If the start date or end date is completely missing, duration will not be calculated. However, an event with completely missing start date will be considered as treatment emergent.

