6.3. Safety Assessments

6.3.1. Adverse Events

All AEs will be collected from the time the subject signs the ICF until the final visit/contact with the subject. Additional safety information, including the definition of an AE and the methods for recording, evaluating, and assessing causality of AEs and the procedures for completing and transmitting SAE reports are provided in [Section 8](#).

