7.1. Visit 1; Screening Period (Day -34 to Day -1)

After the subject has signed the Informed Consent Form (ICF), potential study subjects will undergo Screening procedures and assessments to confirm eligibility to participate in the study. Screening assessments will include the following:

- Demography recording
- Serum pregnancy test (females of child-bearing potential)
- Medical history recording
- ECG recording
- Brief physical examination (including weight, height, and body mass index [BMI])
- Vital signs measurements
- HADS assessment
- PGA score
- %BSA affected calculation; subject’s scalp, palms, and soles should be excluded from the %BSA calculations used to determine patient’s eligibility
- Blood sample collection for clinical laboratory tests (serum chemistry, hematology, diagnostic tests)
- Urinalysis
- AE recording (from the time the ICF is signed)
- Concomitant medication recording (from the time ICF is signed)

To determine subject eligibility at Screening, a single repeat of tests or procedures may be allowed at the discretion of the Investigator. The Medical Monitor should be consulted if needed.

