### **12.9.1 Adverse Events**

AE terms will be coded using the MedDRA dictionary. A treatment-emergent AE (TEAE) is defined as an AE that starts after the first dose of study medication. For subjects not rolling over to Open-label study, all reported AEs will be included in the Double-Blind phase summaries. For subjects rolling over to the Open-label study, all AEs with an onset date on or before the Week 12 visit date will be included in the Double-Blind phase summaries.

If relationship to treatment is missing, the event will be conservatively treated as related to study drug. Missing severity will be imputed to the highest severity level (most severe).

All AEs will be listed by treatment and by subject, detailing the verbatim term given by the investigator, the preferred term (PT), system organ class (SOC), onset date and time, end date and time, duration (days), CTCAE grade, outcome, relationship to study drug/treatment, action taken with study drug/treatment, other action taken to treat the event, seriousness and criteria for seriousness. Serious AEs (SAEs), TEAEs leading to study discontinuation, TEAEs related to study drug will also be listed separately. The following adverse event of special interest (AESIs) will be identified and listed separately: contact dermatitis, folliculitis, and headache.

AEs will be summarized by treatment and overall as incidence rates of:

- Any AE
- Any TEAE
- Any AESIs
- Any treatment-related TEAE, including definitely, probably, and possibly related
- Any TEAE leading to study drug discontinuation
- Any SAE (non-Fatal)
- Any serious TEAE
- Death
- Treatment-related Serious TEAE
- Serious TEAE leading to study drug discontinuation

Individual PTs will be summarized by treatment according to the following:

- All TEAEs by SOC in alphabetical order and PT in descending order of combined frequency (also for treatment-related TEAEs, TEAEs leading to study discontinuation and serious TEAEs)
- All TEAEs by SOC, PT, and maximum CTCAE grade
- All TEAEs by SOC, PT, and maximum causality (not related, related) to the study drug

In addition, TEAEs and serious TEAEs will be summarized by SOC (alphabetical order) and PT (descending order) for the following subgroups:

- Age (<65 and >= 65 years old)
- Sex
- Race (White, Other)

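### For adverse events with an incomplete start date, SAP 9 assigns treatment-emergent status without checking the end date, so an event already over before the first dose can count as a TEAE

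*SAP*

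**What the plan says.** SAP 9 introduces its adverse event date rules with their purpose: "To calculate duration of Adverse Events, the following rules will be used where applicable to impute partial or completely missing start dates or end dates". The same rules also settle whether an event is treatment-emergent. Three of them can make an event with an incomplete start date a TEAE:

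- **Day missing, month and year equal to those of the first dose.** The first of the month is imputed. If that precedes dosing, "the date of first dose will be used as the new estimated date. The AE will be considered as a treatment-emergent AE (TEAE".
- **Day and month both missing.** No date is imputed and no duration is calculated, but the event is treatment-emergent "if the year of start is the same or greater than the year of the first dose date".
- **Start completely missing.** No duration is calculated, but "an event with completely missing start date will be considered as treatment emergent".

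The end-date rule acts only on incomplete end dates: "If only the day is missing for an end date, the last day of the month will be imputed". Its only cap is the last study visit. It compares the end date neither with the first dose nor with the imputed start.

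The definition in SAP 12.9.1 is: "A treatment-emergent AE (TEAE) is defined as an AE that starts after the first dose of study medication". Protocol 10.4.3 likewise limits AE summaries to events after the first dose. Collection starts earlier. Protocol 6.3.1 says: "All AEs will be collected from the time the subject signs the ICF until the final visit/contact with the subject". Protocol 7.1 lets screening run from Day -34 to Day -1.

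**The concern.** Events that start and resolve during screening will be in the database. If such an event has an incomplete start date of one of the three kinds above, SAP 9 makes it treatment-emergent even when its recorded end date shows it was over before any study drug was applied. That contradicts the definition in SAP 12.9.1, because an event that ended before the first dose cannot have started after it.

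The consequences are in the safety outputs. The event enters the TEAE tables. If its relationship field is blank, SAP 12.9.1 also counts it as related to study drug. TEAE duration is a protocol safety endpoint, and for each AESI (contact dermatitis, folliculitis, headache) SAP 12.9.1 plans summaries of earliest onset day and duration and a Kaplan-Meier figure of time to first event. Under the day-missing rule a pre-dose headache would appear there with a false Day 1 onset and possibly an impossible duration.

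**Working it through.** The plan gives no figure to reproduce, so the check applies the SAP 9 rules literally to dated examples.

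**Inputs.** The three start-date rules and the end-date rule come from SAP 9, the TEAE definition from SAP 12.9.1, and the 34-day pre-dose window from Protocol 7.1. The SAP states no AE duration formula, so both usual conventions are carried as assumptions: end - start + 1, and end - start. The first dose is set at 20 March for illustration.

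| Recorded start | Recorded end | Start used | TEAE? | end - start + 1 | end - start |
|---|---|---|---|---|---|
| Unknown day, March | 5 March | 20 March | Yes | 5 - 20 + 1 = -14 | 5 - 20 = -15 |
| Unknown day, March | 19 March | 20 March | Yes | 19 - 20 + 1 = 0 | 19 - 20 = -1 |
| Unknown day, March | Unknown day, March (31 March imputed, if not after the last visit) | 20 March | Yes | 31 - 20 + 1 = 12 | 31 - 20 = 11 |
| Year only, same as first dose | 5 March | None | Yes | Not calculated | Not calculated |
| Completely missing | 5 March | None | Yes | Not calculated | Not calculated |
| 1 March (complete) | 5 March | 1 March | No | 5 - 1 + 1 = 5 | 5 - 1 = 4 |
| Unknown day, February | 5 March | 1 February | No | Positive | Positive |

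Rows 1, 2, 4 and 5 are wrong: the recorded end precedes the first dose, yet the event is a TEAE. Row 3 is not an error, because the end cannot be shown to precede the first dose. Rows 6 and 7 are classified correctly.

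**Extreme of the day-missing rule.** First dose on the 31st and end on the 1st of the same month: 1 - 31 + 1 = -29, or 1 - 31 = -30.

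**Is row 1 a special case?** Take every first-dose date in 2019, a day-missing start in that month, and every complete end date earlier in the same month. A month of n days contributes n(n - 1)/2 combinations:

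- seven months of 31 days: 7 x 465 = 3255
- four months of 30 days: 4 x 435 = 1740
- February: 378
- total: 5373

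All 5373 are classed as TEAEs. With end - start + 1, the duration is zero when the event ended the day before the first dose, which gives 365 - 12 = 353 combinations. The other 5373 - 353 = 5020 are negative. With end - start, all 5373 are negative. These are counts of date patterns, not an estimate of how often they occur.

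**Comparison within the SAP.** SAP 12.5 separates prior from concomitant medications mainly by stop date. The AE rules have no equivalent check.

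**The case against.** Four points can be made for the plan.

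- **Convention.** Counting an event of unknown onset as treatment-emergent is a usual conservative choice. That stands where timing is uncertain. It does not stand where the recorded end date already settles the matter, and a negative duration is not conservative in any sense.
- **Data cleaning.** Protocol 9 has inconsistencies queried, and SAP 5 requires data review and validation before lock. An end date without a start day is an obvious query target, and Protocol 8.1.3 asks sites to collect duration for every AESI and onset for headache. This should reduce the number of cases. But the rules in SAP 9 exist for dates that remain incomplete, and the recorded data need not be inconsistent: the imputation creates the conflict.
- **AESI durations.** SAP 12.9.1 takes each subject's maximum duration, so a negative value reaches the summary only if that subject has no other occurrence of the same AESI with a longer calculable duration. This is correct and limits the visible effect. It does not protect the onset or time-to-event outputs.
- **Interpretation.** An event that ended before dosing cannot depend on the assigned treatment, so the error favours neither arm in expectation. SAP 12.9 plans no formal safety comparisons. Both points stand.

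A reader might also infer that every screening event resolved before dosing becomes a TEAE, or that any start in the first-dose year is enough. The documents support neither. Complete start dates, and day-missing starts in an earlier month, are handled correctly, and the year rule applies only when both day and month are missing.

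**Conclusion.** The point holds for adverse events with an incomplete start date of the three kinds listed. As written, SAP 9 classes such an event as treatment-emergent even when its recorded end precedes the first dose, contrary to SAP 12.9.1, and no other section supplies an end-date check.

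Zero or negative durations are narrower. They need a missing start day in the first-dose month together with a complete end date before the first dose. Whether the value is, for example, -14 or -15 depends on a formula the SAP does not state. The other two rules calculate no duration.

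The documents give no rate of incomplete AE dates, so the number affected is unknown and probably small. It would be tempting to size the problem from the length of screening relative to treatment. That would at best describe how many events start before dosing, not how many have an incomplete start date and a recorded pre-dose end. The effect is confined to safety tabulations; no efficacy result is affected.

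**What to change.** Add to SAP 9:

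- If the known end date, or the known end month and year, is before the first dose, the event is not treatment-emergent.
- An imputed start date may not be later than the end date.
- The existing rules that move the start to the first dose or presume treatment emergence apply only when the end date is on or after the first dose, the event is ongoing, or its end cannot be shown to precede the first dose.

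Stating the AE duration formula in the same place would remove the ambiguity noted above. In the March example the event would then not be a TEAE, its start would stay at 1 March, and its duration would be 5 days (or 4 under end - start).

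The cost is a short SAP addition and one programming condition, made before unblinding. No new data are needed, and the conservative handling of uncertain onset is kept.

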
 To describe the effect of tapinarof cream, 1% on psoriasis symptom severity and the associated impact on daily activities and attitudes in adults with plaque psoriasis 	
 Change in Peak Pruritus-Numeric Rating Scale (Peak Pruritus-NRS) from Baseline at Weeks 2, 4, 8, and 12 Change over time in psoriasis impact on daily activities, as measured by the Dermatology Life Quality Index (DLQI) total and individual dimension scores Change over time in psoriasis symptoms, as measured by the Psoriasis Symptom Diary (PSD) Change over time in physical component score and mental component score, as measured by the Short Form-36 (SF-36) questionnaire

 To evaluate the safety and tolerability of tapinarof cream, 1% 	
Safety:
 
 Incidence, frequency, and duration of treatment emergent adverse events (TEAEs) and serious adverse events (SAEs)

Objectives	Associated Endpoint
in adults with plaque psoriasis	
• Clinically significant change from Baseline in laboratory values• Clinically significant change from Baseline in vital signs• Mean Local Tolerability Scale (LTS) scores by visit

• To characterize the PK of tapinarof in adults with plaque psoriasis	Pharmacokinetic: 
• Plasma concentration of tapinarof at Weeks 4 and 12

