8.3.2. Follow-Up of Adverse Events

After the initial AE/SAE report, the Investigator is required to proactively follow each subject at subsequent visits/contacts. All SAEs and nonserious AEs will be followed until resolution, until the condition stabilizes, until the event is otherwise explained, or until the subject is lost to follow-up.

The Investigator will assess the outcome of each AE using the following criteria:

- **Recovered/Resolved:** The event has improved or subject recuperated.
- **Recovered/Resolved with sequelae:** The subject has recuperated but retained pathological conditions resulting from the prior disease or injury.
- **Recovering/Resolving:** The event is improving.
- **Not recovered/Not resolved:** The event has not improved or subject recuperated.
- **Unknown:** The outcome of the event is not known, not observed, not recorded, or refused.
- **Fatal:** Termination of life as an outcome of the AE.

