At each level of summarization, a subject will be counted once if he/she reported one or more events. The severity of TEAEs and relationship to study drug will be summarized in a similar manner. For summaries of relationship to study drug, a subject will be classified according to the closest relationship. For summaries of TEAE CTCAE grade, a subject will be classified according to the worst grade.

For AESIs, summarization will be more extensive, reflecting the more detailed information collected. Information summarized will include number of events per subject, earliest onset day, duration (in days), causality, grade and seriousness of AESIs, outcome, actions taken with study drug, assorted physical characteristics of the AESIs, and demographic/baseline characteristics and PGA status of the subjects experiencing them. Each type of AESI will be summarized separately. If a subject has more than one treatment-emergent occurrence of an AESI, the subject's maximum duration, highest levels of causality and seriousness, maximum grade and generally the most extreme level of each characteristic will be summarized. If an AESI was ongoing at EOS, it will not be included in the duration summary.

A Kaplan-Meier figure will be generated for each AESI of time to first event. Subjects not experiencing the AESI will be censored at the date of study completion or discontinuation.

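### SAP section 9 resets a day-missing AE end date to the last study visit even when the recorded end month is later, so the duration of those events is understated

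*SAP*

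**What the plan says.** SAP section 9, under the imputation of AE start and end dates, sets out how duration is derived when dates are partial.

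- Start date, day missing: "If only the day is missing for a start date, the 1 st of the month will be imputed". If that falls before first dose, it is moved, but only on a condition: "while the known month and year match the month and year of the first dose, the date of first dose will be used".
- End date, day missing: "If only the day is missing for an end date, the last day of the month will be imputed". Then: "If the new estimated date falls after the date of last study visit, the date of last study visit will be used". No condition on month or year is attached.
- The cap date for subjects who roll over is early: "Last study visit is defined as the Week 12 visit for those who elect to participate in the open-label long-term study". For the other subjects it names, it is the Week 16 Follow-up visit. Early withdrawers are not mentioned.
- If day and month are both missing, nothing is imputed and no duration is calculated.

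Protocol section 2 makes duration a safety endpoint: "Incidence, frequency, and duration of treatment emergent adverse events (TEAEs) and serious adverse events (SAEs)". Protocol section 8.3.2 states: "All SAEs and nonserious AEs will be followed until resolution", with stabilisation, another explanation or loss to follow-up as alternative stopping points.

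SAP section 12.9.1 puts duration in the by-subject AE listing and summarises it only for AEs of special interest (AESIs). For a subject with repeat occurrences that summary takes the "maximum duration, highest levels of causality and seriousness". It leaves out AESIs still ongoing at end of study (EOS).

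**The concern.** An end date recorded as a month after the last visit is incomplete, but it does carry information: the event ended no earlier than the first of that month. The cap discards this and substitutes a date that the record rules out. The start-date rule avoids the equivalent mistake through its month-and-year check, so the omission looks like a drafting gap.

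The result is also inconsistent between subjects. The cap is written only for dates with a missing day. Two events that ended on the same day, one with the day recorded and one without, get different durations.

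The events concerned are those that outlast the study, so the error shortens long events. At stake is the accuracy of a descriptive safety endpoint. No hypothesis test is involved.

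**Working it through.** The plan states no figure on this point, so there is nothing to reproduce. The check applies the SAP rule to example dates and compares the result with the range that the recorded month allows.

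**Assumptions.** The SAP gives no formula for AE duration. I use end minus start plus 1, the same form as its days-exposed definition in section 12.4. All calendar dates are illustrative.

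**Can such dates arise?** Yes. SAP section 12.9.1 counts, for rollover subjects, every AE with onset up to the Week 12 visit date. Protocol section 8.3.2 continues follow-up of AEs beyond scheduled visits where needed. An event that starts shortly before Week 12 can therefore have an end month after it.

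**Example 1.** Start 10 May (complete), last visit 15 May, end recorded as July with the day missing.

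- Imputed end before the cap: 31 July. This is after 15 May, so the cap sets the end to 15 May.
- SAP duration: 15 − 10 + 1 = 6 days.
- Shortest duration the record allows (end 1 July): 22 days in May + 30 in June + 1 = 53 days.
- Longest (end 31 July): 22 + 30 + 31 = 83 days.
- Understatement: 53 − 6 = 47 to 83 − 6 = 77 days.
- The same event with a complete end date of, say, 20 July is not capped: 22 + 30 + 20 = 72 days.

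**Example 2.** First dose 15 January 2020, so Week 12 (Day 85) is 8 April and Week 16 (Day 113) is 6 May. AE start 20 March.

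| Last visit | Recorded end month | SAP duration (days) | Range the record allows (days) | Understatement (days) |
|---|---|---|---|---|
| Week 12, 8 April | May | 20 | 43 to 73 | 23 to 53 |
| Week 12, 8 April | June | 20 | 74 to 103 | 54 to 83 |
| Week 12, 8 April | July | 20 | 104 to 134 | 84 to 114 |
| Week 16, 6 May | June | 48 | 74 to 103 | 26 to 55 |

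With the Week 12 cap the SAP value is 20 days whichever later month was recorded.

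**Where the cap is harmless.** If the end month in Example 2 is April, the month of the Week 12 visit, the cap again gives 20 days. The record allows 13 to 42, so the imputed date agrees with the recorded month. The defect is confined to recorded months later than the visit month.

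**The case against.** The strongest reply is that the cap may never reach a summary table. An AESI with an end month after the last visit was still ongoing at that visit. If the EOS exclusion in SAP section 12.9.1 is judged by date, the event drops out of the only duration summary and the cap affects the listing alone. This stands as a limit on the consequence. However, the SAP does not say whether ongoing status is judged by date or by the recorded outcome. On the second reading the truncated value enters the summary.

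Protocol section 8.1.3 also has sites collect duration for each AESI, and the SAP does not say whether its summary uses that field or the derived dates. That is a further uncertainty about reach, and it does not defend the rule.

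Frequency is unknown. AEs are collected until the final visit, contacts occur about every two weeks, and section 8.3.2 allows follow-up to stop short of resolution. Late partial end dates are possible, but the documents do not show that they will be common.

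A reader might go further and infer that AE duration as a whole is wrong in both directions, because first-of-month starts and last-of-month ends can stretch a short event to a full month. The documents do not support that. The convention is pre-specified, agrees with the recorded months, errs towards longer durations and touches only partial dates. Nor does the AESI summary generally select stretched values, since its maximum rule applies only to repeat occurrences in one subject.

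**Conclusion.** The end-date cap is wrong as written for one subset: AEs whose end date lacks the day and whose recorded end month is later than the last study visit. For these the imputed date contradicts the data and duration is too short, by 47 to 77 days in Example 1 and by 23 to 114 days across Example 2. These sizes depend on the assumed dates and the inclusive day count. The documents give no rate of partial dates, so no effect on a group mean or median can be stated.

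The by-subject AE listing is affected in any case. The AESI duration summary is affected only if it uses the derived dates and ongoing status at EOS is not judged by date. Efficacy, power and AE incidence are unaffected, and safety data are not formally compared. This is a small correction worth making, and it does not call the safety analysis as a whole into question.

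**What to change.** In SAP section 9:

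1. Apply the last-visit cap only when the recorded end month and year equal those of the last study visit, mirroring the start-date rule.
2. When the recorded month is later, choose one treatment and state it. Either keep the recorded month (83 days in Example 1; 103 days for a June end in Example 2), or class the event as ongoing at EOS and leave it out of the AESI duration summary. Apply the same choice to complete end dates, so that a missing day does not change how an event is handled. Say in section 12.9.1 how ongoing status at EOS is judged.
3. Define the last study visit for early withdrawers as the last visit actually attended. Protocol section 7.5 gives them an Early Termination visit and Table 1, footnote a, also a Follow-Up visit, so naming only one of them could cap too early.

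Flagging imputed durations in the listing would help but is optional. The first-of-month and last-of-month imputation can stay.

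The cost is a few sentences and a few lines of derivation code before database lock. No data collection changes.
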